3.4.1 Study-Staff-Generated Capillary Testing Goal

Study-staff-generated capillary results will be analyzed in the same fashion as the ISO accuracy objective for subject-generated capillary (fingerstick) results for only evaluable results from subjects with diabetes, and the same acceptance criteria applied.

Study-staff-generated capillary results will be analyzed in the same fashion as the FDA accuracy objective for subject-generated capillary (fingerstick) results for only evaluable results from ALL subjects, and the same acceptance criteria applied.

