1.2 FDA Objective – Accuracy with All Subjects Included

For the FDA accuracy objective, a result (MeterBG) is considered accurate if:

$$|RD| = 100 * |\text{MeterBG} - \text{LabBG}| / \text{LabBG} \leq 15\%, \text{ regardless of the value of LabBG.}$$

Assuming $n = 350$ evaluable results, $X_c = 333$ results would be required to satisfy the accuracy criteria. At $P_0 = 96.65\%$, there is approximately a 95% chance of satisfying the FDA 15% objective. Conversely, at $P_a = 92.81\%$, there is approximately a 95% chance of failing to satisfy the FDA accuracy objective.

The FDA guidance has a second criterion, that 99% of n evaluable results must have $|RD| \leq 20\%$. Inasmuch as the two criteria are considered separately, there is no consideration for multiplicity. For the $n = 350$, the 20% criterion requires a critical value of $X_c = .99 * 350$

$= 346.5 \rightarrow 347$. For this critical value and sample size, with $P_0 = 99.61\%$, there is approximately a 95% chance of satisfying the FDA 20% criterion. Conversely, there is approximately a 95% chance of failing to satisfy the 20% criterion if the chance of obtaining a result within $\pm 20\%$ of corresponding comparator measurement is only 97.8%.

Note that each glucose result obtained with the evaluation device will be considered either 'accurate' or 'not accurate', where accuracy depends on the particular test criterion.

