3.3 FDA Objectives

3.3.1 95% within $\pm 15\%$

With $n = 350$, at least $X_c = 333$ measurements must be within $\pm 15\%$ of LabBG. This requirement is equivalent to testing the hypothesis:

$$H_0: \Pr\{|RD| \leq 15\% \} < 0.9664$$

against the hypothesis:

$$H_1: \Pr\{|RD| \leq 15\% \} \geq 0.9664$$

with $\Pr\{\text{reject } H_0 | p=0.9664\} \approx 0.9488$

3.3.2 99% within $\pm 20\%$

With $n = 350$, at least $X_c = 347$ measurements must be within $\pm 20\%$ of LabBG. This requirement is equivalent to testing the hypothesis:

$$H_0: \Pr\{|RD| \leq 20\% \} < 0.9960$$

against the hypothesis:

$$H_1: \Pr\{|RD| \leq 20\% \} \geq 0.9960$$

with $\Pr\{\text{reject } H_0 | p=0.9960\} \approx 0.9466$

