2.1 Primary Objectives, ISO 15197:2013

2.1.1 Fingerstick Test: Obtain T-PLUS BGMS performance data in the hands of lay users with diabetes using fingerstick capillary blood obtained with Microlet NEXT® lancing device.

- **95% of glucose results shall fall within $\pm 15\text{mg/dL}$ of laboratory method at glucose concentration $<100 \text{ mg/dL}$ and within $\pm 15\%$ at glucose concentrations $\geq 100 \text{ mg/dL}$**

2.2 Secondary Objectives: Failure of any sub objectives listed below does not constitute the failure of the secondary objective.

Study objectives 2.2.1 to 2.2.3 are in accordance with **ISO 15197:2013, Section 8**, and apply to data collected ONLY from **subjects who have diabetes**.

2.2.1 Alternative Site Test (AST): Obtain T-PLUS BGMS performance data in the hands of lay users with diabetes using capillary blood from the palm site obtained with Microlet NEXT lancing device with the AST endcap. Acceptance criteria will be the same as fingerstick 2.1.1.

2.2.2 Venous Blood Test: Obtain T-PLUS BGMS performance data using venous blood from lay users with diabetes. Acceptance criteria will be the same as fingerstick 2.1.1.

¹ Self-Monitoring Blood Glucose Test Systems for Over-the-Counter Use, Draft Guidance for Industry and Food and Drug Administration Staff. Issued 30Nov2018, Food and Drug Administration, USA. (abbreviated FDA SMBG:2018)

² In vitro diagnostic test systems – Requirements for blood-glucose monitoring systems for self-testing in managing diabetes mellitus. Issued 15 May2013, International Organization for Standardization, Switzerland. (abbreviated ISO 15197:2013)

2.2.3 Subject Questionnaire 1: The questionnaire will include statements about the T-PLUS BGMS instructions for use (product labeling) and ease of use of the basic blood testing operations of the meter system. These statements will be given a rating by the subjects with diabetes (1=strongly disagree, 2=disagree, 3=neutral, 4=agree, 5=strongly agree), and frequency distributions will be tabulated. Results will be compared to the following criteria:

- **Acceptance criteria: There must be at least a 90% probability that a user would respond with a score of 3 or higher to statements concerning instructions for use or ease of use.***

Study objectives 2.2.4 to 2.2.7 are in accordance with **FDA SMBG: 2018**, and apply to data collected from ALL subjects (**subjects who are diabetic and Naïve**).

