2.2.9 **Study staff test (two analyses: all subjects and for subjects with diabetes):** Obtain T-PLUS BGMS performance data in the hands of trained study staff testing subjects' fingerstick blood obtained with Microlet NEXT lancing device.

- **Test the hypothesis that there is at least a 95% probability that meter results would be within $\pm 15\text{mg/dL}$ of laboratory method at glucose concentrations $<100\text{ mg/dL}$ and within $\pm 15\%$ at glucose concentrations $\geq 100\text{ mg/dL}^{**}$**

2.2.10 **Subject Questionnaire 2 (only subjects with diabetes):** This questionnaire for subjects with diabetes will include statements about user preferences and feedback regarding the features of the T-PLUS BGMS in routine diabetes management. These statements will be given a rating by the subjects (1=strongly disagree, 2=disagree, 3=neutral, 4=agree, 5=strongly agree), and frequency distributions will be tabulated.

- **Acceptance criteria: There are no pass/fail criteria for Questionnaire 2.**

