11.1 Primary Objective, 2.1.1, and Secondary Objectives 2.2.1, 2.2.2 (ISO 15197)

The percentages of results from PWD subjects satisfying the ISO 15197 accuracy definition:

95% of glucose results shall fall within $\pm 15\text{mg/dL}$ of laboratory method (LabBG) at glucose concentration $<100\text{ mg/dL}$ and within $\pm 15\%$ at glucose concentrations $\geq 100\text{ mg/dL}$

will be computed.

If $n = 315$ PWD subjects (90% of 350), the critical value is $0.95*315 = 299.25 \approx 300$. Thus, the critical value is associated with testing the hypothesis:

H0: $\text{Pr}\{\text{ISO Accurate result}\} < 0.9678$

against the alternate:

H1: $\text{Pr}\{\text{ISO Accurate result}\} \geq 0.9678$

(Pardo, 2014)⁵

The power to reject H0 at $\text{Pr}\{\text{ISO Accurate result}\} = 0.9678$ is approximately 0.9490.

Other Secondary Accuracy Objectives

Internal Accuracy Objectives: 2.2.8, 2.2.9

2.2.8 Criterion 1

Define criterion 1:

T-Plus Meter result with $\pm 12.5\text{mg/dL}$ if $\text{LabBG} < 100\text{mg/dL}$, or

T-Plus Meter result within $\pm 12.5\%$ of corresponding Lab result (LabBG), if $\text{LabBG} \geq 100\text{mg/dL}$

Test the hypothesis:

H0: $p = \text{Pr}\{\text{meter result satisfies criterion 1}\} < 0.95$

H1: $p = \text{Pr}\{\text{meter result satisfies criterion 1}\} \geq 0.95$

The critical value, X_c (minimum number of X “successes”) is determined to be the smallest number such that $\text{Pr}\{X \geq X_c | p=0.95\} \leq 0.95$. For $n = 315$, $X_c = 294$ (power ≈ 0.9263).

2.2.9 Criterion 2

Define criterion 2:

T-Plus Meter result with $\pm 15\text{mg/dL}$ if $\text{YSI} < 100\text{mg/dL}$, or

T-Plus Meter result within $\pm 15\%$ of corresponding YSI result, if $\text{YSI} \geq 100\text{mg/dL}$

Test the hypothesis:

H0: $p = \text{Pr}\{\text{meter result satisfies criterion 2}\} < 0.95$

H1: $p = \text{Pr}\{\text{meter result satisfies criterion 2}\} \geq 0.95$

⁵ Pardo, S., (2014) Equivalence and noninferiority Testing for Quality, Manufacturing, and Test Engineers, Chapman&Hall/CRC, Boca Raton

The critical value, X_c (minimum number of X “successes”) is determined to be the smallest number such that $\Pr\{X \geq X_c | p=0.95\} \leq 0.95$. If $n = 315$, $X_c = 294$ (power ≈ 0.9263). If $n = 350$, $X_c = 327$ (power ≈ 0.9246)

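### Protocol and SAP set different pass rules for the staff-test objective (2.2.9), and SAP 3.4 and 3.5 misstate thresholds for related secondary tests

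*SAP*

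**What the plan says.** **Staff test, protocol.** Objective 2.2.9 is headed "Study staff test (two analyses: all subjects and for subjects with diabetes". Section 11.1 gives both analyses a single accuracy definition: within ±15 mg/dL when the laboratory value is below 100 mg/dL, and within ±15% otherwise. It tests H0: p < 0.95. The critical value "is determined to be the smallest number such that" the chance of reaching it at p = 0.95 is at most 0.95. The printed counts are 294 of 315 and 327 of 350.

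**Staff test, SAP.** Section 3.4.1 is the SAP's only staff-test rule. For subjects with diabetes, "Study-staff-generated capillary results will be analyzed in the same fashion as the ISO accuracy objective for subject-generated capillary (fingerstick) results", with the same acceptance criteria; SAP 3.1 sets these at 300 of 315. For the whole study population, diabetic and naïve together, staff results are handled "in the same fashion as the FDA accuracy objective for subject-generated capillary (fingerstick) results", and the FDA pass rule is carried over with it. SAP 1.2 introduces that objective with "For the FDA accuracy objective, a result (MeterBG) is considered accurate if" and then requires ±15% whatever the laboratory value. SAP 3.3.1 adds the count: "With $n = 350$, at least $X_c = 333$ measurements must be within" ±15%. SAP 3.3.2 has a second FDA rule, 347 of 350 within ±20%.

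**±12.5 objective (2.2.8).** SAP 3.4 names no population and gives n = 350, Xc = 327. SAP 1.3 restricts the objective to subjects with diabetes, and SAP 1.3, SAP Table 1.1 and protocol 11.1 give n = 315, Xc = 294. The heading of protocol 2.2.8 also restricts it to subjects with diabetes, but its double-asterisk footnote refers to the pool of all subjects.

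**General rule.** SAP 3.5 says that the critical value is always 95% of the evaluable sample size.

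**The concern.** A staff-test result is to be declared pass or fail in two populations, and the two documents would declare it differently. For subjects with diabetes the definition is the same and the count differs. For all subjects both differ. Below 100 mg/dL, ±15% is narrower than ±15 mg/dL (at 60 mg/dL it is ±9 mg/dL), so the SAP rule is the stricter one throughout. It is also unclear whether the ±20% rule applies to staff results.

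Protocol 11.0 refers to the SAP for the analysis, but 11.1 then prints its own hypotheses and counts, and no order of precedence is given. If the rule is chosen after the results are seen, the verdict is open to challenge.

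SAP 3.4 and 3.5 matter less but concern the same thing. SAP 3.5 is where an analyst would look for the count when the evaluable n is not exactly 315 or 350, which is likely given the enrolment goal of at least 370.

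**Working it through.** **Inputs.** n and Xc come from protocol 11.1, SAP 1.1–1.3, SAP 3.1 and SAP 3.3. The SAP's design accuracies, 96.79% (ISO) and 96.65% (FDA ±15%), come from SAP Table 1.1. Everything is exact binomial: T(n, r, p) = P(X ≥ r), X ~ Bin(n, p).

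**1. The plan's own figures reproduce.**

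- T(315, 294, 0.95) = 0.9263 and T(315, 293, 0.95) = 0.9536, so 294 is the smallest count with probability at most 0.95.
- T(350, 327, 0.95) = 0.9246 and T(350, 326, 0.95) = 0.9513, so 327 follows in the same way.
- ISO: 0.95 × 315 = 299.25, rounded up to 300; T(315, 300, 0.9679) = 0.9502.
- FDA ±15%: 0.95 × 350 = 332.5, rounded up to 333; T(350, 333, 0.9665) = 0.9500.

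The arithmetic is sound in both documents. The rules differ.

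**2. Staff test, count difference alone.** The verdicts split when 294 to 299 of 315, or 327 to 332 of 350, are accurate. Split probability = T(n, protocol Xc, p) − T(n, SAP Xc, p).

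| True p | 294 of 315 | 300 of 315 | Split | 327 of 350 | 333 of 350 | Split |
|---|---|---|---|---|---|---|
| 0.95 | 0.9263 | 0.4898 | 0.4365 | 0.9246 | 0.5148 | 0.4098 |
| 0.96 | 0.9912 | 0.8019 | 0.1892 | 0.9920 | 0.8316 | 0.1604 |
| SAP design value | 0.9994 | 0.9502 | 0.0492 | 0.9991 | 0.9500 | 0.0491 |
| 0.97 | 0.9997 | 0.9700 | 0.0298 | 0.9998 | 0.9799 | 0.0200 |
| 0.98 | 1.0000 | 0.9993 | 0.0007 | 1.0000 | 0.9997 | 0.0003 |

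The design-value row uses 0.9679 for n = 315 and 0.9665 for n = 350. Splits are taken before rounding.

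**3. All subjects, adding the definition difference.** Every result within ±15% also meets the protocol definition, so a SAP pass is always a protocol pass. Let p be the rate meeting the protocol definition and p′ the rate within ±15% at every level. Then split = T(350, 327, p) − T(350, 333, p′). The documents give no p′, so these values are assumptions, with p = 0.97:

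- p′ = 0.970: 0.9998 − 0.9799, split 0.0200
- p′ = 0.965: 0.9998 − 0.9305, split 0.0693
- p′ = 0.960: 0.9998 − 0.8316, split 0.1682

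**4. At the enrolment target.** Assume all 370 are evaluable and 90% (333) have diabetes. The protocol's binomial rule gives 345 of 370 and 311 of 333. The SAP's 95% rule gives 0.95 × 370 = 351.5, rounded up to 352, and 0.95 × 333 = 316.35, rounded up to 317.

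**5. SAP 3.4.** 327 is right for n = 350 but belongs to the wrong population. For the 315 subjects with diabetes the same rule gives 294.

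**6. SAP 3.5.** Taken literally, 95% of n gives 333 of 350 for FDA ±20%, against 0.99 × 350 = 346.5, rounded up to 347. It gives 300 of 315 for the ±12.5 objective, against 294 (294/315 = 93.3%).

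**The case against.** The textual conflict on the staff test is not in dispute. The case on the other side is about weight.

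- **Consequence.** The objective is internal, and protocol 2.2 says "Failure of any sub objectives listed below does not constitute the failure of the secondary objective". The split also runs one way: following the SAP cannot produce a staff-test pass that the protocol would deny. Both points stand and limit the harm. The reverse remains possible: an analyst following the protocol could report a pass that the SAP would call a fail.
- **Size.** The 5% at the design values is nearly built in, because those values were chosen to give a 95% chance of meeting the SAP count. It does not forecast how often the documents will disagree. The 41–44% figures need a true accuracy of exactly 95%, and the p′ values are assumed. This stands; the figures should be read as a range.
- **±20% for staff results.** SAP 3.4.1 names the FDA objective in the singular, as SAP 1.2 does for the 15% rule, but refers to acceptance criteria in the plural. The SAP uses that same plural for tests with only one threshold. The grammar settles nothing, which is why the plan should say.
- **SAP 3.4 and 3.5.** Other sections state the right counts, and SAP 3.5 can be read as covering only ISO and FDA ±15%, for which it is correct. No careful analyst would apply 333 of 350 to the ±20% rule. That is fair, and these two are minor. The sentence is still unqualified, in a section headed as general comments on the hypothesis tests.

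**Conclusion.** The plan is wrong as written, for secondary objectives only; it should be fixed. Protocol 2.2.9/11.1 and SAP 3.4.1 give different staff-test rules: 294 against 300 of 315 for subjects with diabetes, and 327 against 333 of 350 for all subjects, the latter with a different accuracy definition below 100 mg/dL. The chance that the count difference alone decides the verdict depends on an unknown true accuracy. It is about 5% at the SAP's design values, negligible at 98%, 16–19% at 96% and 41–44% at 95%. For all subjects the definition difference can raise it, to 7–17% under the assumed rates.

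These figures assume independent results and exactly 315 or 350 evaluable. They leave out the ±20% rule, which would make the SAP stricter still. SAP 3.4 and 3.5 are lesser errors in thresholds that other sections give correctly. The primary objective is untouched.

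**What to change.** Before the accuracy results are analysed:

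1. **Staff test.** State one accuracy definition and one count rule for each population, identically in SAP 3.4.1 and protocol 2.2.9 and 11.1. Say explicitly whether the ±20% rule applies to staff results.
2. **±12.5 objective.** Correct SAP 3.4 to subjects with diabetes, n = 315, Xc = 294, with the binomial rule applied at the actual evaluable n. Correct the footnote marker on protocol 2.2.8.
3. **SAP 3.5.** Limit the 95% sentence to ISO and FDA ±15% (0.95n, rounded up). Give 0.99n, rounded up, for FDA ±20%. Give the binomial rule for 2.2.8 and, if the sponsor keeps it there, for 2.2.9.

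The cost is wording in SAP 3.4, 3.4.1 and 3.5 and in protocol 2.2.8, 2.2.9 and 11.1. Data collection and sample size do not change.

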3.5 Some Additional Comments about Hypothesis Tests

Power and risk calculations were made based on the assumption that $n = 315$ for the ISO accuracy objective, and for $n = 350$ for the FDA accuracy objective. It is possible that the total number of results may differ from the minimum requirement, depending on the numbers of subjects actually enrolled and the number of evaluable results. The critical value is always 95% of the total sample size of evaluable results. However, power statements made earlier were based on $n = 315$ or $n = 350$, so these statements may only be approximate.

No adjustment will be made for multiplicity. Each test will be evaluated without regard to the results of any other test.

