1.1 ISO 15197:2013 Objective – Accuracy in People with Diabetes

Let MeterBG = meter blood glucose result;

LabBG = laboratory method (YSI) comparator blood glucose result.

$$D = \text{MeterBG} - \text{LabBG}$$

$$RD = 100 * (\text{MeterBG} - \text{LabBG}) / \text{LabBG}$$

Assume 315 evaluable results from people with diabetes. The ISO 15197:2013 acceptance criterion is that 95% of those evaluable results must satisfy the accuracy criteria:

$$|D| = |\text{MeterBG} - \text{LabBG}| \leq 15 \text{ mg/dL}, \text{ for } \text{LabBG} < 100 \text{ mg/dL}$$

or

$$|RD| = 100 * |\text{MeterBG} - \text{LabBG}| / \text{LabBG} \leq 15\%, \text{ for } \text{LabBG} \geq 100 \text{ mg/dL}.$$

With $n = 315$, $X_c = 300$ results would be required to satisfy the accuracy criteria. At $P_0 = 96.79\%$, there is approximately a 95% chance of satisfying the ISO objective. Conversely, at $P_a = 92.77\%$, there is approximately a 95% chance of failing to satisfy the ISO objective.

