2.2.4 Fingerstick Test: Obtain T-PLUS BGMS performance data in the hands of **lay users with diabetes and naïve users** (without diabetes) from fingerstick capillary blood using Microlet NEXT lancing device.

- **95% of glucose results shall fall within $\pm 15\%$ of laboratory method across the entire tested range**
- **99% of glucose results shall fall within $\pm 20\%$ of laboratory method across the entire tested range**

2.2.5 Alternative Site Test (AST): Obtain T-PLUS BGMS performance data in the hands of **lay users with diabetes and naïve users** (without diabetes) from the palm site using the Microlet NEXT lancing device with the AST endcap. Acceptance criteria will be the same as fingerstick 2.2.4.

2.2.6 Samples will adequately span the claimed measuring range. At least ten unaltered samples with blood glucose concentration at the lower limits of the measuring range (less than 80 mg/dl) and at least ten unaltered samples at the upper limit measuring range (greater than 250 mg/dl) will be obtained for each anatomical site (i.e. fingerstick & palm).

2.2.7 Subject Questionnaire 1: The questionnaire will include statements about the T-PLUS BGMS instructions for use (product labeling) and ease of use of the basic blood testing operations of the meter system. These statements will be given a rating by all of the subjects (1=strongly disagree, 2=disagree, 3=neutral, 4=agree, 5=strongly agree), and frequency distributions will be tabulated. Results will be compared to the following criteria:

- **Acceptance criteria **: There will be no pass/fail criteria for FDA: SMBG 2018**

*This is a “total population” (hypothesis test) requirement for the pool of all subjects with diabetes.

** This is a “total population” (hypothesis test) requirement for the pool of all subjects (naïve and diabetic).

Study objectives 2.2.8 to 2.2.10 below are internal objectives and apply to data collected from all subjects OR subjects who have diabetes, as specified for each objective.

2.2.8 **Fingerstick Test (only subjects with diabetes):** Obtain T-PLUS BGMS performance data in the hands of lay users with diabetes using fingerstick capillary blood obtained with Microlet NEXT lancing device.

- **Test the hypothesis that there is at least a 95% probability that meter results would be within $\pm 12.5\text{mg/dL}$ of laboratory method at glucose concentrations $<100\text{ mg/dL}$ and within $\pm 12.5\%$ at glucose concentrations $\geq 100\text{ mg/dL}^{**}$**

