4.3 Subject Recruitment

4.3.1 The following additional population criteria are study goals with the site recruiting to meet these goals:

1. Enrolment: At least 370 subjects
2. At least 70% of subjects will be younger than age 65.
3. Ten to fifteen % (10-15%) of subjects will be people without diabetes.
4. At least 20% of subjects (with diabetes) will have type 1 diabetes.

4.3.2 There must be at least 350 total evaluable fingerstick self-test results and at least 350 total evaluable AST palm self-test results. ISO 15197:2013 criteria requires at least 100 evaluable results each for fingerstick self-test results, AST palm self-test results, study staff performed fingerstick blood and venous blood tests.

4.3.3 In Addition, per FDA SMBG:2018, at least 10 unaltered evaluable subject fingerstick and AST palm blood samples will be < 80 mg/dL and 10 will be > 250 mg/dL (by capillary YSI assay). Subject enrollment will continue until the required evaluable samples are collected

4.3.4 No laboratory tests (e.g., pregnancy) are required to assure qualification. Subjects' verbal responses will be accepted and recorded on forms which will serve as source documents for the electronic data capture (EDC) system.

4.3.5 The site study staff will perform the following when the subject arrives at the clinical trial site:

1. Complete the informed consent process.
2. Assign a unique number to each subject.

4.3.6 The study staff will document subject demographics (including both screen-failed and enrolled subjects), diabetes history, medical conditions and medications information. Subjects will also be asked when they last ate, took diabetes medications, and performed vigorous exercise.

4.3.7 If the subject does not have diabetes, the outside of the subject folder will be labeled to indicate that venipuncture should NOT be performed.

4.3.8 According to the randomization schedule, subjects will be assigned to use one of three Contour Plus test strip lots (R,B or G) throughout the visit.

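### SAP 3.5 fixes every critical value at 95% of evaluable results, which contradicts the 99% rule for FDA ±20% and the binomial rule for the internal ±12.5 objective

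*SAP*

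**What the plan says.** SAP 3.5 recalls that power was computed at n = 315 (ISO) and n = 350 (FDA). It then allows for other counts, "It is possible that the total number of results may differ from the minimum requirement", and gives the rule for them: "The critical value is always 95% of the total sample size of evaluable results". It names no criterion and makes no exception.

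Elsewhere the documents use three different rules for accuracy pass marks:

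- **95% of n, rounded up.** ISO (SAP 1.1): "With $n = 315$, $X_c = 300$ results would be required to satisfy the accuracy criteria". FDA ±15% (SAP 1.2): "Assuming $n = 350$ evaluable results, $X_c = 333$ results would be required to satisfy the accuracy criteria".
- **99% of n, rounded up.** FDA ±20% (SAP 1.2): "The FDA guidance has a second criterion, that 99% of n evaluable results must have" a relative difference of at most 20%. Protocol 2.2.4 has the same share, "99% of glucose results shall fall within $\pm 20\%$ of laboratory method across the entire tested range", as do SAP 3.3.2 and protocol 11.2. The printed mark is 347 of 350.
- **Binomial rule.** For the ±12.5 objective, protocol 11.1 says that Xc "is determined to be the smallest number such that" Pr{X ≥ Xc | p = 0.95} ≤ 0.95. The printed marks are 294 of 315 (SAP 1.3, protocol 11.1) and 327 of 350 (SAP 3.4).

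The text after SAP Table 1.1 adds that critical values depend on the actual sample size, but gives no formula.

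**The concern.** The counts for which marks are printed may well not be the counts obtained. Protocol 4.3.1 sets "Enrolment: At least 370 subjects" with a floor of 350 evaluable fingerstick self-tests, and enrolment continues until enough low and high glucose samples are in hand. Once n moves off 315 or 350, the analyst needs a general rule, and SAP 3.5 is where the SAP addresses that situation.

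Its rule errs in opposite directions for the two criteria it does not fit. For FDA ±20% it is too lenient, allowing about 5% of results beyond ±20% where the criterion allows 1%. For ±12.5 it is too strict. It therefore cannot be defended as uniformly conservative. A pass/fail threshold fixed in advance should not leave the analyst choosing between two statements once the data are in.

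**Working it through.** All probabilities are exact binomial upper tails, Pr{X ≥ Xc | n, p}.

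**1. The plan's own figures reproduce.**

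| Criterion | n | Rule | Xc | Check |
|---|---|---|---|---|
| ISO | 315 | 0.95 × 315 = 299.25, up | 300 | pass 0.9502 at p = 0.9679 |
| FDA ±15% | 350 | 0.95 × 350 = 332.5, up | 333 | pass 0.9500 at p = 0.9665 |
| FDA ±20% | 350 | 0.99 × 350 = 346.5, up | 347 | pass 0.9505 at p = 0.9961; fail 0.9500 at p = 0.978 |
| ±12.5 | 315 | binomial, p = 0.95 | 294 | tail 0.9263 at 294; 0.9536 at 293 |
| ±12.5 | 350 | binomial, p = 0.95 | 327 | tail 0.9246 at 327; 0.9513 at 326 |

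No printed mark is miscalculated. As shares of n, the ±12.5 marks are 294/315 = 93.3% and 327/350 = 93.4%, and the ±20% mark is 347/350 = 99.1%. Only the ISO and FDA ±15% rows follow a 95% rule.

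**2. The SAP 3.5 rule set against each criterion's own rule.** Counts other than 315 and 350 are illustrative assumptions.

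FDA ±20%, pass probability at p = 0.978, the value for which SAP Table 1.1 gives a 95% chance of failing:

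| n | Xc at 99% of n | Pass | Xc at 95% of n | Pass |
|---|---|---|---|---|
| 350 | 347 | 0.050 | 333 | 0.999 |
| 360 | 357 | 0.043 | 342 | 0.9995 |
| 365 | 362 | 0.040 | 347 | 0.999 |
| 370 | 367 | 0.037 | 352 | 0.999 |

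At n = 365 the 99% rule tolerates 365 − 362 = 3 results beyond ±20%; the 95% rule tolerates 365 − 347 = 18.

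±12.5, pass probability at p = 0.95:

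| n | Xc by protocol 11.1 | Pass | Xc at 95% of n | Pass |
|---|---|---|---|---|
| 315 | 294 | 0.926 | 300 | 0.490 |
| 324 | 302 | 0.940 | 308 | 0.546 |
| 330 | 308 | 0.930 | 314 | 0.515 |

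For every n from 100 to 400, the 95% mark differs from both the 99% mark and the protocol 11.1 mark, so no plausible count makes the rules coincide.

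**3. When a conclusion would change.** The two marks give different answers only if the observed count lies between them: 347 to 361 of 365 for ±20%, or 302 to 307 of 324 for ±12.5. For ±12.5 at n = 324, the chance of that is 0.940 − 0.546 = 0.39 at p = 0.95, about 0.15 at p = 0.96 and about 0.02 at p = 0.97. For ±20% at n = 365 and p = 0.978, it is 0.999 − 0.040 = 0.96.

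**4. The staff test.** Protocol 11.1 (Criterion 2) applies the binomial rule to staff results within ±15 mg/dL or ±15%: 294 of 315 for subjects with diabetes, 327 of 350 for all subjects. SAP 3.4.1 applies the ISO acceptance criteria to subjects with diabetes (300 at n = 315) and the FDA criteria to all subjects (333 within ±15% and 347 within ±20% at n = 350). The two documents therefore disagree on this mark even at the planned counts.

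**The case against.** The best defence is that SAP 3.5 was meant only for the two 95% criteria. It refers to the ISO accuracy objective and the FDA accuracy objective. SAP 1.2 introduces the latter through the 15% limit and treats ±20% as a second criterion. Read that way, the sentence is true at every n. Taken literally, it would also overrule the printed 347 of 350, which can hardly be intended. This has force but does not settle the matter: SAP 3.3 puts both FDA criteria under one heading of objectives, the sentence allows no exception, and SAP 3.5 comes after the ±12.5 objective in 3.4.

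It is also fair that other passages supply the right rules. A reader might infer that SAP 3.5 is the only place that says how marks change with n, or that an analyst would be bound to pass a device with 5% of results beyond ±20%. The documents do not support either inference. SAP 1.2 and protocol 11.2 express the ±20% requirement as a share of n, and protocol 11.1 gives the ±12.5 rule in general form. For ±20% the defect is a contradictory sentence, not a missing rule.

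The defence is weaker for ±12.5. The SAP contains no general rule for that objective, and its hypothesis is itself framed at 95%, so an analyst working from the SAP alone could take 95% of n as the intended mark.

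On consequence, both affected criteria are secondary. Protocol 2.2 says that failing one sub-objective does not fail the secondary objective as a whole. An over-strict ±12.5 mark could not create a false claim of success.

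**Conclusion.** The contradiction is real and limited to two secondary criteria, FDA ±20% and internal ±12.5. The primary ISO objective and FDA ±15% are unaffected at any n, and every printed critical value is correct, so nothing here should be read as an error in the sample size or in Table 1.1.

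The ±20% figures at n = 365 (347 against 362) and the ±12.5 figures at n = 324 (308 against 302) show what literal use of SAP 3.5 would do. They are not predictions. They assume those evaluable counts, independent results with a common success probability, and an analyst who follows SAP 3.5 over the other passages. A conclusion then changes only if the count falls in the gap. The ±20% error would be the larger but is the easier to catch; ±12.5 is the more exposed. This should be fixed, but it does not threaten the trial's main conclusion.

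**What to change.** Replace the sentence in SAP 3.5 with wording such as: *For n evaluable results, the critical value is 0.95n rounded up for the ISO and FDA ±15% criteria, 0.99n rounded up for the FDA ±20% criterion, and, for the ±12.5 objective, the value given by the protocol 11.1 rule at the actual n.* Stating the rounding also makes explicit what the printed marks already do.

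In the same edit, reconcile the staff test between protocol 11.1 and SAP 3.4.1, stating one accuracy definition and one critical-value rule for each of its two populations.

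The cost is one SAP sentence plus the staff-test reconciliation, made before the data are analysed. No new data, sample size or design change is needed.
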